#### 4.1.1 Treatment Stopping Criteria

At Week 48, all subjects will have an assessment of Treatment Stopping Criteria. Any subjects who meet the below Treatment Stopping Criteria, will discontinue their assigned treatment including NrtI, and continue with off-treatment follow-up through Week 96, unless they meet the NrtI-restart criteria (see Section 4.1.2). Decisions to discontinue assigned treatment and undergo off-treatment follow-up will be based on laboratory results from blood samples collected at the Week 48 visit. Subjects will remain on their assigned oral agents (ie, VBR+NrtI for Groups 1 and 2; NrtI for Group 3) until Week 48 laboratory results required for Treatment Stopping Criteria assessment are available.

Treatment Stopping Criteria are:

- ALT  $<$  2  $\times$  ULN, and

- HBV DNA < LLOQ, *and*
- HBsAg < 100 IU/mL

Subjects who do not meet the Treatment Stopping Criteria with Week 48 laboratory results will continue treatment with NrtI alone and will remain in follow-up through Week 96.

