#### **9.10.4 Management of Alanine Aminotransferase (ALT) Elevations**

All subjects participating in the study will be closely monitored for ALT elevations and/or signs of potential decline in hepatic function (see [Figure 7](#)). Subjects experiencing ALT elevations  $\geq 2\times$  Baseline (Day 1) or on-treatment nadir and  $>2\times$  ULN during study treatment or during post-treatment follow-up should be closely monitored with regular Unscheduled Visits every 1 to 2

weeks at the discretion of the Investigator. At these visits, the following laboratory tests will be performed: ALT, AST, total bilirubin (if total bilirubin is elevated, reflex to direct bilirubin), serum albumin, INR and creatine kinase. The Investigator will determine if other Unscheduled Visit assessments should be performed. Additionally, the following guidance is provided for management of subjects with ALT elevations:

- ALT Elevation Without Declining Hepatic Function
  - All subjects with an ALT elevation on treatment, defined as ALT  $>2\times$  Baseline or on treatment nadir and  $\geq 10\times$  ULN, should have the ALT findings confirmed within 3 days of receipt of the original results. All subjects should return for an Unscheduled Visit.
  - If the ALT elevation is confirmed, then an additional Unscheduled Visit will be performed to further evaluate the subject. At this visit, the following laboratory tests will be performed: ALT, AST, total bilirubin (if total bilirubin is elevated, reflex to direct bilirubin), serum albumin, INR, creatine kinase, HBV DNA, quantitative HBV serologies (HBeAg [reflex qualitative HBeAg if quantitative HBeAg is negative] and HBsAg [reflex qualitative HBsAg if quantitative HBsAg is negative]), HAV immunoglobulin M (IgM), HCV RNA, HDV RNA, HEV IgM, ANA, smooth muscle antibodies and anti-LKM1 antibodies, EBV DNA, CMV DNA, HSV DNA, and total IgG. The Investigator will determine if other Unscheduled Visit assessments should be performed.
    - If an intercurrent illness is determined to be causal, subjects with an ALT elevation without declining hepatic function and without contraindications may continue treatment and the intercurrent illness should be treated as deemed medically appropriate by the Investigator.
    - Subjects with an ALT elevation without declining hepatic function and without contraindications may continue treatment with study drug under close observation.

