All subjects with ALT elevation without or with declining hepatic function should continue to be followed on their regular study visit schedule, with the addition of unscheduled visits as described above. If the posttreatment ALT elevation has not substantially resolved by the last study follow-up visit, subjects should continue to return to clinic as deemed medically appropriate by the Investigator, in consultation with the Sponsor until the ALT elevation is documented to be either resolved or resolving (defined as consistent ALT declines of 10% or more or normalization of ALT) on at least 2 successive visits.

Following cessation of study drug treatment under this protocol, all subjects will be closely followed for ALT elevations and/or signs of potential decline in hepatic function. This applies to all subjects whether they prematurely discontinue study drug or complete the study treatment per protocol. Any subject with a post-treatment ALT elevation without evidence of declining hepatic function or a post-treatment ALT elevation with evidence of declining hepatic function as defined above, will be evaluated as noted above.

If 5 or more subjects meet these flare management criteria, the relevant regulatory agencies will be notified, and subsequent steps will be determined after consultation with these agencies.

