#### **7.2.1.2. Summaries of Laboratory Abnormalities**

A summary (number and percentage of subjects) for treatment-emergent laboratory abnormalities will be provided by lab test and treatment group; subjects will be categorized according to the most severe postbaseline abnormality grade for a given laboratory test.

Treatment-emergent lab abnormalities will be summarized based on the Safety Analysis Set. Tables will be created per study phase (i.e. On-Treatment Phase, Off-Treatment Phase, and NrtI-Restart Phase).

For all summaries of laboratory abnormalities, the denominator is the number of subjects with nonmissing postbaseline values in each phase.

The maximum post-baseline grade in each phase will be tabulated for each laboratory test, and percentages will be based on the number of subjects with a post-baseline evaluation of the specific laboratory test. The laboratory abnormalities during the follow-up period will also be summarized.

A by-subject listing of graded laboratory abnormalities will be provided by subject ID number and visit in chronological order. This listing will include all test results that were collected throughout the study for the lab test of interest, with all applicable severity grades displayed.

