#### **7.2.3.2. ALT Elevation with Declining Hepatic Function**

Subjects with confirmed ALT elevation with evidence of declining hepatic function should be discontinued prematurely from study treatment. This is defined as:

- ALT elevation  $\geq 2 \times$  Baseline (Day 1) or nadir and  $> 2 \times$  ULN AND
- Direct bilirubin increase to  $\geq 2 \times$  Baseline (Day 1) and  $\geq 2 \times$  ULN OR
- Albumin decline  $\geq 0.5$  g/dL from Baseline OR international normalized ratio (INR)  $> 2 \times$  Baseline (Day 1) OR
- Symptoms of liver inflammation (eg, fatigue, weakness, lack of appetite, nausea, vomiting, jaundice or discolored feces)

The number of subjects meeting the above criteria will be summarized by treatment group. Clinical signs or symptoms of liver inflammation will not be included in the summary. For individual laboratory tests, subjects will be counted once based on the most severe postbaseline values. For the composite criteria, subjects will be counted once when the criteria are met at the same visit. The denominator is the number of subjects in the Safety Analysis Set who have nonmissing postbaseline values. A listing of subjects who met at least 1 of the above criteria will be provided.

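### SAP 7.2.3.2 counts ALT elevation with declining hepatic function by arm without a phase split, so drug effects and NrtI withdrawal can be mixed

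*Combined protocol and SAP*

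**What the plan says.** SAP 7.2.3.2 defines the composite (an ALT rise together with a direct bilirubin, albumin or INR change; symptoms are left out of the table) and then states: "The number of subjects meeting the above criteria will be summarized by treatment group". For individual tests, "subjects will be counted once based on the most severe postbaseline values". On the denominator: "The denominator is the number of subjects in the Safety Analysis Set who have nonmissing postbaseline values". No phase is named. A by-subject listing is also planned.

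The neighbouring safety sections do name the phase. SAP 7.1.6 (adverse events), 7.2.1.2 (graded laboratory abnormalities) and 7.2.2 (direct bilirubin) each carry the instruction "Tables will be created per study phase", and 7.2.1.2 also uses a per-phase denominator.

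Protocol 4.1.1 provides that subjects who meet the Treatment Stopping Criteria at Week 48 "will discontinue their assigned treatment including NrtI, and continue with off-treatment follow-up through Week 96". Protocol 9.10.4 applies its ALT surveillance both on and off drug: subjects with a qualifying rise "during study treatment or during post-treatment follow-up should be closely monitored".

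**The concern.** The primary objective is the safety of the combination, and this table is where a reader would look for serious liver signals by arm. Two different causes can put a subject in it: an effect of VBR or AB-729, or loss of viral control after NrtI is withdrawn by design. Withdrawal is not randomized. It follows response, because a subject must bring HBsAg below the level required for entry. If one regimen lowers HBsAg more, more of its subjects stop NrtI and more are exposed to withdrawal flares. A by-arm count over all postbaseline data could then make the more active regimen look more hepatotoxic.

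**Working it through.** The plan states no expected count for this table, so there is no figure of its own to reproduce. The allocation does check: 60 in 2:1:1 gives 60 × 2/4 = 30, 60 × 1/4 = 15 and 15, as in protocol Table 7.

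**1. Does the text pool phases?**

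| SAP section | Content | Phase split stated? | Denominator |
|---|---|---|---|
| 7.1.6 | TEAEs | yes | Safety Analysis Set |
| 7.2.1.2 | graded laboratory abnormalities | yes | postbaseline values in each phase |
| 7.2.2 | direct bilirubin | yes | Safety Analysis Set |
| 7.2.3.2 | ALT elevation with declining function | no | any postbaseline value |

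SAP 7.3 (vital signs) counts follow-up visits as postbaseline visits, so the word does not by itself mean on treatment. Followed as written, 7.2.3.2 runs from first dose to end of study.

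**2. Does stopping depend on arm?** Entry requires HBsAg ≥100 IU/mL (protocol 5.2); stopping requires <100 IU/mL (4.1.1). A decline of *D* log10 brings a subject below 100 only if baseline is below 100 × 10^*D*.

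| Source in protocol | Mean decline *D* | Baseline must be below |
|---|---|---|
| Table 3, VBR+ETV, Week 48 | 0.2 | 158 IU/mL |
| 2.3.3.3, AB-729 180 mg single dose, Week 12 | 0.980 | 955 IU/mL |
| 2.3.3.3, AB-729 60 mg single dose, Week 12 | 0.989 | 975 IU/mL |
| 2.3.3.3, AB-729 60 mg every 4 weeks, Week 12 | 1.10 | 1,259 IU/mL |
| 2.3.3.3, AB-729 90 mg single dose, Week 12 | 1.23 | 1,698 IU/mL |

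On mean declines, a much wider range of baselines would qualify in Groups 1 and 3 than in Group 2. The ALT and HBV DNA criteria must also be met, so these are limits on one criterion only.

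**3. What does this do to the count?** Let *d* be the probability of an on-drug event, *s* the fraction of an arm stopping all antivirals, and *w* the probability of an event after stopping. Treating the two causes as independent, the pooled proportion is 1 − (1 − *d*)(1 − *sw*) = *d* + (1 − *d*)*sw*. Two arms with the same *d* then differ by (1 − *d*) × *w* × (*s*A − *s*B). This is zero only if *w* = 0 or the stopping fractions are equal (leaving aside *d* = 1). The documents give neither *s* nor *w*. What they do fix is the weight of one case: 100/15 = 6.7 percentage points in Group 2 or 3, and 100/30 = 3.3 in Group 1, if all planned subjects are in the denominator.

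**4. Is phase alone enough?** No. The Off-Treatment Phase (SAP 3.6.3) begins after VBR and AB-729 end. It therefore holds both subjects who stopped everything and subjects who carry on with NrtI. Treatment action separates them, and SAP 3.6.5 and 6.1.2 already use it.

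**The case against.** Pooling is not stated as a decision. SAP 3.6.3 says in general that analyses follow three phases, 7.2.3.1 speaks of ALT elevation on treatment, and 7.2.3.2 opens with premature discontinuation of study treatment. One could infer that a phase split was meant. That is a fair reading of intent. However, the other sections repeat the split and 7.2.3.2 instead gives its own unphased denominator, so a programmer following the text would pool. It is best described as an omission.

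Much of the separation exists elsewhere. TEAEs, graded ALT and direct bilirubin are tabulated per phase, ALT change is summarized by phase and treatment action, and listings show the hepatic cases and each stopping decision. This stands and limits the harm. None of these, however, gives the composite by phase.

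A reader might infer that the regulator notification in protocol 9.10.4 is also faulty: "If 5 or more subjects meet these flare management criteria, the relevant regulatory agencies will be notified", and the paragraph before it covers "Any subject with a post-treatment ALT elevation without evidence of declining hepatic function or a post-treatment ALT elevation with evidence of declining hepatic function". The documents do not support that. The rule leads to notification and consultation; it neither stops the trial nor assigns cause, and withdrawal is part of the strategy under study. Probabilities that withdrawal alone would produce five cases need numbers of stoppers and flare rates that the documents do not give, and SAP 1.2 made the stopping criteria inapplicable to subjects reaching Week 48 after the February 2023 announcement.

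A reader might also infer that stopping is almost confined to Groups 1 and 3. That is too firm. The VBR mean comes from 12 treatment-naive, HBeAg-positive subjects with individual changes from −1.5 to +0.7 log10. The AB-729 figures are Week 12 results, not 48 weeks of dosing every 8 weeks. Nor do the restart criteria in 4.1.2 predict flares; they provide for them.

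**Conclusion.** The point holds for the SAP table. As written, 7.2.3.2 can mix on-drug hepatic events with events after planned NrtI withdrawal, and the mixing is likely to differ by arm because stopping depends on HBsAg response. The arm imbalance is inferred from mean declines in other studies and is not stated in the documents. The size cannot be given. Early termination limited the number of stoppers by an unstated amount, so the effect may be small, but with arms of 15 and 30 a single case is visible. The notification rule is not shown to be wrong.

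It would also go too far to rest the safety conclusion on the On-Treatment table alone. That phase ends at the last AB-729 dose plus 56 days, or the last VBR dose plus 1 day if later, while HBsAg declines were still reported 12 weeks (84 days) after a single AB-729 dose. Delayed AB-729 effects could therefore fall off treatment.

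**What to change.** In SAP 7.2.3.2, produce the table by study phase (On-Treatment, Off-Treatment, NrtI-Restart) and, within the Off-Treatment Phase, by treatment action: all antivirals stopped versus NrtI continued. Take as denominator the subjects with nonmissing postbaseline values in that phase, and count each subject once per phase.

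Use the On-Treatment table as the main by-arm comparison and show the off-treatment events beside it. Add two notes: delayed AB-729 effects may appear off treatment, and off-treatment comparisons between arms are not randomized because stopping depends on response. Since the SAP is final, the change can be recorded in the Synoptic CSR, as the SAP Introduction provides. Leave the five-subject notification in protocol 9.10.4 as it is.

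The cost is one further split of a planned table on phases and treatment actions already in use, and smaller cells.

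A separate matter in the same definition: the INR criterion is a multiple of Baseline above 1.5 in protocol 9.10.4 and above 2 in SAP 7.2.3.2. The two must be reconciled; until then the table and the protocol rule do not count the same events.

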    - If ALT is rising at the confirmatory visit, subjects should return for an Unscheduled Visit every 2 to 5 days until the ALT elevation has stabilized. At these visits, the following laboratory tests will be performed: ALT, AST, total bilirubin (if total bilirubin is elevated, reflex to direct bilirubin), serum albumin, INR, creatine kinase, HBV DNA, quantitative HBV serologies (HBeAg [reflex qualitative HBeAg if quantitative HBeAg is negative] and HBsAg [reflex qualitative HBsAg if quantitative HBsAg is negative]). The Investigator will determine if other assessments specified in [Section 8.4](#) should be performed. Subjects whose ALT has stabilized should continue to be monitored weekly (or more frequently, as deemed necessary by the Investigator) until ALT values return to normal or Baseline levels.
    - Subjects with an ALT elevation without declining hepatic function and without contraindications should discontinue study drug if the ALT remains persistently elevated for  $>4$  weeks
- ALT Elevation With Declining Hepatic Function

[figure not shown]
- Subjects with confirmed ALT elevation with biochemical evidence of declining hepatic function should be discontinued from study treatment. This is defined as:
  - ALT elevation  $\geq 2 \times$  Baseline or nadir and  $> 2 \times$  ULN AND
    - Direct bilirubin increase to  $\geq 2 \times$  Baseline and  $\geq 2 \times$  ULN OR
    - Albumin decline  $\geq 0.5$  g/dL OR INR  $> 1.5 \times$  Baseline OR
    - Symptoms of liver inflammation (eg, fatigue, weakness, lack of appetite, nausea, vomiting, jaundice, or discolored feces)
- Subjects with evidence of declining hepatic function should return for an Unscheduled Visit every 2 to 5 days until the relevant laboratory values stabilize. Subjects whose hepatic function has stabilized should continue to be monitored weekly (or more frequently as deemed necessary by the Investigator) until the relevant laboratory values return to normal or Baseline.

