## 1. INTRODUCTION

Study ABI-H0731-204 is a randomized Phase 2a, multicenter, open-label, multiple-cohort study evaluating the safety and antiviral activity of Vebicorvir (VBR) and AB-729 in combination with other chronic hepatitis B virus (HBV) infection (cHBV) treatments in subjects with cHBV. The target population is male or female subjects, 18 to 50 years of age, inclusive, with no evidence of cirrhosis or end-stage liver disease. Cohort 1 is prespecified and will enroll virologically-suppressed subjects on nucleos(t)ide reverse transcriptase inhibitor (NrtI) therapy with hepatitis B virus “e” antigen (HBeAg) negative cHBV. Approximately 60 subjects will be enrolled in Cohort 1 of this study. Up to 2 additional cohorts, with approximately 60 subjects per cohort, may be added in future protocol amendments, for a maximum sample size of approximately 180 subjects.

This statistical analysis plan (SAP) describes the statistical analysis methods and data presentations to be used in tables, figures, and listings (TFLs) in the clinical study report (CSR) for Study ABI-H0731-204. This SAP is based on the study protocol Amendment 1, dated 27 October 2021 and the electronic case report form (eCRF). In February 2023, Assembly and Arbutus jointly made the decision to discontinue study ABI-H0731-204, following the observation that AB-729 in dual combination with NrtI alone and as a triple combination with VBR promoted similar on-treatment declines in HBsAg, as has been observed in other AB-729 studies. Thus, there appears to be limited additional benefit to subjects continuing in the post-treatment study period as currently defined in the protocol. The study was prematurely terminated after every active subject completed 48-week treatment period.

The SAP will be finalized before database lock. Only key safety and efficacy endpoints will be performed. Any changes made after the finalization of the SAP will be documented in the Synoptic CSR.

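### The composite count in SAP 7.2.3.2 leaves out the symptom route and requires criteria to be met at one visit, so it is narrower than the definition in protocol 9.10.4

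*Combined protocol and SAP*

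**What the plan says.** Protocol 9.10.4 introduces the definition with "Subjects with confirmed ALT elevation with biochemical evidence of declining hepatic function should be discontinued from study treatment. This is defined as". It then requires ALT at least 2 times Baseline or nadir and above 2 times ULN, together with any one of four further criteria. Three are laboratory criteria: direct bilirubin, albumin and INR. The fourth is "Symptoms of liver inflammation (eg, fatigue, weakness, lack of appetite, nausea, vomiting, jaundice, or discolored feces". Nothing is said about the components falling at the same visit.

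SAP 7.2.3.2 reproduces this structure, symptoms included, and promises a by-group count of subjects meeting the criteria. Two sentences then narrow the count. The first is "Clinical signs or symptoms of liver inflammation will not be included in the summary". The second is "For the composite criteria, subjects will be counted once when the criteria are met at the same visit". The section also plans counts for individual laboratory tests based on the most severe postbaseline value, and adds "A listing of subjects who met at least 1 of the above criteria will be provided". SAP section 1 states: "This SAP is based on the study protocol Amendment 1, dated 27 October 2021".

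**The concern.** The SAP gives a definition and then counts something narrower. A subject with a qualifying ALT value and jaundice alone meets protocol 9.10.4 and the SAP's own list but cannot enter the composite. The same is true of a subject whose ALT criterion is met at one visit and whose bilirubin, albumin or INR criterion is met only at another.

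Safety is the primary objective, the summaries are descriptive, and the protocol ties this classification to stopping study treatment. A reader of the report would expect the by-group count to match the subjects whom the protocol classifies this way. Unless the row says what it counts, it may not.

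**Working it through.** The SAP gives no figure to reproduce, so the check sets the two texts side by side and then tests the logic.

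| Element | Protocol 9.10.4 | SAP 7.2.3.2, list | SAP 7.2.3.2, composite count |
|---|---|---|---|
| ALT | ≥2× Baseline or nadir and >2× ULN; confirmed | Same thresholds; confirmed in the lead-in | Confirmation not mentioned |
| Direct bilirubin | ≥2× Baseline and ≥2× ULN | Same | Included |
| Albumin | Decline ≥0.5 g/dL | Same, from Baseline | Included |
| INR | >1.5× Baseline | >2× Baseline | Included at the SAP value |
| Symptoms | Sufficient with ALT | Listed | Excluded |
| Timing | None stated | None stated | Same visit |

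**Logic check.** Describe each visit by ALT met or not, bilirubin met or not, albumin met or not, INR in one of three classes (≤1.5×, >1.5 to 2×, >2× Baseline), and symptoms present or not. That gives 2×2×2×3×2 = 48 states per visit and 48² = 2304 two-visit patterns.

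- Protocol, no timing condition: ALT met at one visit or both in 48² − 24² = 1728 patterns. Remove the 2² − 1² = 3 in which no other criterion is ever met. Result: 1725.
- SAP count: of the 24 states with ALT met, 4 have no qualifying laboratory value (two lower INR classes × symptoms yes or no), so 20 of the 48 states qualify. Result: 48² − 28² = 2304 − 784 = 1520.
- Difference: 1725 − 1520 = 205 patterns meet the protocol and not the SAP count; none go the other way.
- Protocol read as implying concurrence: 23 of 48 states qualify, so 48² − 25² = 2304 − 625 = 1679. The SAP count still omits 1679 − 1520 = 159, through symptoms and INR.

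**Setting the INR difference aside.** With one common INR threshold there are 2⁵ = 32 states and 32² = 1024 patterns. The protocol takes (32² − 16²) − 3 = 765. The SAP count takes 32² − 18² = 700, because 16 − 2 = 14 states qualify. The gap is 65, so aligning the INR threshold alone does not close it.

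**Single cases.**

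| Pattern | Protocol | SAP count |
|---|---|---|
| ALT at visit 1, bilirubin at visit 2 | Yes | No |
| ALT plus symptoms only, same visit | Yes | No |
| ALT plus INR 1.8× Baseline, same visit | Yes | No |
| ALT plus bilirubin, same visit | Yes | Yes |

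The pattern counts test logic only; they are not probabilities or expected numbers of subjects. ALT confirmation was not modelled.

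**Weight of one subject** at the planned arm sizes (SAP 1.3): 1/15 = 6.7% and 1/30 = 3.3%. These show what one subject contributes; they do not estimate how many are omitted.

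**The case against.** The strongest reply is that nothing disappears from the report. A subject whose ALT and bilirubin criteria are met at different visits should appear in the individual-test counts and in the listing. Symptoms recorded as adverse events appear in the tables of SAP 7.1.6, as do events leading to discontinuation of either drug. SAP 7.2.2 summarizes direct bilirubin separately. This stands, and it limits the point to the composite count. It does not repair that count: a listing of anyone meeting at least one criterion mixes isolated laboratory changes with composite events, and it is unclear whether symptoms count among the listed criteria.

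Second, the protocol is silent on timing, and an elevation with declining function can fairly be read as concurrent. Chemistry and coagulation are drawn together at every scheduled visit, and the frequent visits during an ALT elevation make coincidence at some visit more likely. This also stands: omissions through timing may be uncommon. The symptom exclusion does not depend on timing.

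Third, the SAP states the exclusion openly, and the protocol's lead-in speaks of biochemical evidence. Yet both documents go on to list symptoms as a qualifying criterion. Disclosure in the SAP is a reason to label the row accordingly. The documents give a section heading but no table title, so they do not show that the table would be mislabelled.

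A reader might also infer that the count can err only downwards. That is true of the two restrictions, but the counting sentences do not say how confirmation of ALT is applied. If it is not applied, an unconfirmed ALT value with a coincident albumin decline would be counted although it lies outside the protocol's rule.

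**Conclusion.** The point holds for the composite by-group count. That count is narrower than protocol 9.10.4 and than the SAP's own list: symptoms are excluded on any reading, and laboratory criteria met only at different visits are excluded unless concurrence is read into the protocol. The number of subjects affected cannot be computed from the documents, and the net direction of error is not settled while the handling of ALT confirmation is unstated.

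Two stronger readings are not supported. A reader might infer that this is the trial's most serious hepatic outcome; the documents do not rank it so, and clinical decompensation appears as a separate NrtI-restart criterion in protocol 4.1.2. A reader might also link the narrower count to the protocol's notification rule, "If 5 or more subjects meet these flare management criteria, the relevant regulatory agencies will be notified". That rule refers to the protocol's own criteria, and nothing makes it depend on this table. The SAP is dated May 2023, after the February 2023 termination, and serves a synoptic report.

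The differing INR thresholds are a separate, direct contradiction with the amendment that the SAP says it follows. A row labelled as laboratory criteria would not match the protocol's laboratory criteria until the two sections are reconciled.

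**What to change.** In SAP 7.2.3.2:

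1. Keep the present row and label it *laboratory criteria, same visit*. Say whether visit means sampling date or analysis window.
2. Add a row for laboratory criteria met at different visits within one ALT-elevation episode, with the window prespecified. Thirty days is only an example; the documents give no window.
3. Add a separate row for ALT elevation plus adverse event terms matching the protocol's symptom list, with onset in the episode.
4. State how ALT confirmation is applied in each row.
5. Reconcile the INR criterion between SAP 7.2.3.2 and protocol 9.10.4 before the table is produced.

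The cost is a short derivation rule and a term list, using data already collected. Non-specific symptoms such as fatigue will bring in some false positives, so the symptom row should stay separate. Any change after the SAP is final can be documented in the Synoptic CSR, as SAP section 1 provides.
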